#### **Data Analysis:**

Primary analysis is a repeated measures ANOVA to test for a group by time interaction with calculated effect sizes (Cohen's d or Hedges g). The initial analysis will be with a single ISI score. Both study completers and intent-to-treat (ITT) analyses will be conducted, albeit this is an efficacy study therefore the ITT is not necessarily germane to the focus of the work.

Several other variables will be analyzed in similar fashion (breathing event indices, sleep consolidation indices, sleep diary metrics, addition secondary variable measurements). As indicated by post-hoc factor analyses, we may also conduct more advanced multi-variate analyses.

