### ***Synopsis***

Insomnia is the most common sleep disorder affecting millions of adults and is linked to daytime impairment. Insomnia is typically thought of as a symptom, secondary to a primary disorder, and often goes untreated for years. Medication (over the counter or prescription) and sleep hygiene are typical insomnia symptom treatments but they do not address the cause of the insomnia. Newer guidelines view insomnia as a co-morbid disorder needing independent treatment. Recent research has discovered high rates of sleep-disordered breathing (SDB) among insomnia patients; this co-morbid pairing is referred to as "complex insomnia." Several studies have revealed that treatment of SDB decreases insomnia.

This study will determine which of two different types of positive airway pressure (PAP therapy) modes are more effective in reducing sleep breathing events in chronic insomnia patients and in decreasing insomnia severity. Patients presenting to the clinic with a primary complaint of insomnia will be potential participants for this study. Following diagnostic polysomnography (PSG) testing, insomnia patients diagnosed with SDB and meeting inclusion criteria will be randomized to a PAP treatment arm, CPAP or ASV. No experimental devices will be used in this study, both CPAP and ASV are FDA approved for treatment of SDB and are in wide use in the USA. Participants will complete a series of three titration studies with their assigned PAP mode and attend a minimum of five clinical follow-up appointments over a 14-16 week timeframe. Titration PSG studies will assess PAP pressure needs to ensure that patients are receiving optimal therapy at all times during this study. Clinical follow-up visits occur every two weeks at which time objective data download information and subjective measures will be collected. PAP adaptation barriers will be addressed as they arise during the study, because it is important that participants are able to use PAP therapy nightly during participation in this protocol. Baseline scores on insomnia severity, sleep quality, subjective insomnia parameters, sleep related impairment, and quality of life will be compared to outcome measures at the 4 month mark. Pre-treatment and post-treatment objective improvements on sleep studies will also be compared including sleep breathing indices, sleep consolidation indices, and objective data download information.

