## **Summary of Endpoint Objectives:**

### **Primary Endpoint objectives:**

- Change in insomnia severity from baseline to 4 months as measured by the Insomnia Severity Index (ISI)
- Sleep Diary sleep quality rating (8 point Likert scale)
- Global Morning Rating of Nightly Sleep (0-100% scale)
- Change in prospective sleep log data for insomnia parameters (SOL, WASO, SE)

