**Inclusion and Exclusion Criteria:**

## Inclusion criteria:

1.  $\geq 18$  years old
2. Primary complaint of insomnia when presenting at clinic
3. Diagnosis of moderate to severe insomnia through the Insomnia Severity Index (ISI) with a score  $\geq 15$
4. Meet diagnostic criteria of Insomnia Disorder (per American Academy of Sleep Medicine)
5. Diagnosis of SDB, either OSA as determined by an AHI  $\geq 5$  events/hour or UARS with a RDI  $\geq 15$  events/hour and AHI  $< 5$  events/hour
6. Naïve to treatment for sleep-disordered breathing (SDB), including CPAP, APAP, ASV; mandibular repositioning devices (MRDs), and any other nasal or oral therapy with a primary indication of treating SDB
7. Able to fully understand study information in English and sign informed consent

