#### **Questionnaires:**

**Insomnia Severity Index (ISI):** The seven-item questionnaire asks the individual to rate the level of insomnia and perceptions of sleep problems in the last two weeks. Answers must be provided using a scale from 0-4, with 0 reflecting no problem or being very satisfied to 4 indicating a very severe or very dissatisfied experience. Scores are divided into four tiers: 0-7 equates to no clinically significant insomnia, 8-14 equates to subthreshold insomnia, 15-21 indicates moderate severity insomnia, and 22-28 reflects severe insomnia.

**Epworth Sleepiness Scale (ESS):** The ESS is a simple, self-administered questionnaire which provides a measurement of an individual's general level of daytime sleepiness. The responder is asked on a scale of

0–3 to score the likelihood of falling asleep in eight various situations. A higher score indicates a higher level of sleepiness.

**Functional Outcomes of Sleep (FOSQ-10):** The FOSQ-10 is a shorter version of the FOSQ, an instrument used in both research and clinical practice to assess the impact daytime sleepiness has on daily living activities. Global scores range from 5 to 20; scores less than 15 indicative of severe impairment.

**Visual Analog Scale for Fatigue (VAS-F):** A single question on an 11 point Likert scale evaluating daytime fatigue. Higher scores are indicative of more fatigue.

**Visual Analog Scale for Sleepiness (VAS-S):** A single question on an 11 point Likert scale evaluating daytime sleepiness. Higher scores are indicative of more fatigue.

**Insomnia Impairment Index (III):** The III is an 11 item survey based on research diagnostic criteria for insomnia disorder, which measures forms of daytime impairment in relation to nighttime sleep difficulties. It uses a 5 –point Likert scale and is scored with an inter-item average (0 to 4), with higher scores denoting more impairment.

**Fatigue Severity Scale (FSS):** FSS is a 9 question survey on a 7 point Likert scale evaluating daytime fatigue. Higher scores are indicative of more fatigue.

**Sleep Disorder Breathing (SDB-6):** A 6 item survey assessing frequency (on a 4 point scale) and intensity (on a 4 point scale) of end organ symptoms of SDB including cognitive impairment, morning headache, dry mouth, and nocturia.

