### **Power Analysis, Sample Size Data Analysis**

#### **Power Analysis and Sample Size:**

Based on our description in the background (see page 6), our work with ASV anticipates an effect size of at least 1.40 to 1.50 change in insomnia severity with ASV PAP therapy. Whereas, based on our clinical experience we presume that the effect of CPAP on insomnia would yield an effect size range between 0.50 and 0.70. Thus, the average net effect between ASV and CPAP use would be ~0.80 effect size. Using a resource specific to clinical research(77)in order to calculate power and sample size estimates, we used a beta of .90 for two tailed significance testing at .05 which arrived at 26 patients per group, or a total sample of 52. Therefore, using the less stringent criteria of beta .80, we believe our sample size allotments of 25 per group or 50 total should prove more than sufficient for this protocol.

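### Free improvement: adjust the primary ISI comparison for baseline ISI (ANCOVA at week 14-16) instead of relying on an unadjusted group-by-time test

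*Combined protocol and SAP*

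**What the plan says.** The Data Analysis section gives the primary method: "Primary analysis is a repeated measures ANOVA to test for a group by time interaction". It adds: "The initial analysis will be with a single ISI score". No covariate is named there or elsewhere, and the levels of the time factor are not listed.

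Two places point to a pre/post comparison:
- The first primary endpoint is "Change in insomnia severity from baseline to 4 months as measured by the Insomnia Severity Index (ISI").
- The Synopsis says: "Baseline scores on insomnia severity, sleep quality, subjective insomnia parameters, sleep related impairment, and quality of life will be compared to outcome measures" at the 4-month mark.

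Three places show that ISI or outcomes in general are collected more often. Follow-up Visits has the ISI completed at each appointment, Titration #2 has all follow-up scales completed at the retitrations, and the Protocol abstract describes tracking daily or every two weeks for the final comparison.

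A baseline ISI must exist for every patient, because entry requires "Diagnosis of moderate to severe insomnia through the Insomnia Severity Index (ISI) with a score" of at least 15. Under Third Encounter, eligibility is confirmed at step 2 and randomization is step 5. The diary week with the Global Morning Rating, the III and the FSS are baseline questionnaires at step 6.

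The sample size section assumes that "the average net effect between ASV and CPAP use would be ~0.80 effect size", and settles on 25 per group at 80% power. For the remaining outcomes, "Several other variables will be analyzed in similar fashion".

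**The concern.** A group-by-time test with two time points compares mean change between arms. Each patient's baseline is subtracted in full, whatever its actual relation to the follow-up score. Patients here are selected for a high ISI, so the follow-up score may well move less than one point per baseline point. Subtracting the whole baseline then adds noise. In a trial of 50 with almost no power in reserve, a pre-randomization score that every patient already has is not used to best effect. Leaving the time levels unnamed also leaves open which test is primary.

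**Working it through.** **Inputs from the documents:** effect 0.80, two-sided 0.05, 25 per group. **Not given, so assumed and varied:** the baseline and follow-up SDs, their correlation, and which SD the 0.80 refers to.

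**1. The plan's own figure.** With effect 0.80 and two-sided 0.05, the t test needs 34 per group for 90% power. The stated 26 per group is the answer for 80%. At 25 per group the noncentrality is 0.80 × √(25/2) = 2.83 on 48 df, and power is 79.1% (80.7% by normal approximation). So 79% is the starting point, with 0.80 taken on the SD of change.

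**2. Identity with the change score.** On simulated two-time-point data the interaction F and the squared t on change were both 7.2736 (p = 0.0096).

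**3. Variances.** Let sb and sf be the baseline and follow-up SDs among enrolled patients, and ρ their correlation.
- Change score: sb² + sf² − 2ρ·sb·sf
- ANCOVA: sf²(1 − ρ²)
- Difference: (sb − ρ·sf)², which is never negative. It is zero only when the slope ρ·sf/sb equals 1.

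For ANCOVA at N = 50, I used 47 df and multiplied the variance by 47/46 for estimating the slope. The effect is then 0.80/√(ratio × 47/46), where ratio is ANCOVA variance over change variance.

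**4. SDs set directly, sf = 5.** Example with sb = 3.0 and ρ = 0.3: ratio = 22.75/25.00 = 0.91, effect = 0.830, a gain of 2.8 points. Change in power, in points:

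| sb | ρ = 0.3 | ρ = 0.5 | ρ = 0.7 |
|---|---|---|---|
| 2.7 | +1.5 | −0.8 | +1.0 |
| 3.0 | +2.8 | −0.4 | −0.1 |
| 3.3 | +4.2 | +0.4 | −0.8 |
| 3.5 | +5.3 | +1.2 | −0.9 |

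The losses sit where the slope is about 0.8 to 1.2. With sb = 3.5 and ρ = 0.7, for example, the slope is 1.00 and the ratio 12.75/12.75 = 1.

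**5. Entry rule modelled.** Integer ISI was restricted to 15-28 (the scale's top band is "15-21 indicates moderate severity insomnia, and 22-28 reflects severe insomnia"), with latent mean 14 to 20 and latent ρ 0.3 to 0.7. A latent SD near 5 is suggested by the Background: (16.8 − 9.7)/1.40 = 5.07 and (19.0 − 11.9)/1.50 = 4.73. This holds only if d there is mean change over SD, and the second sample was already restricted on ISI.
- Latent SD 5 at both times: variance ratio 0.79 to 0.95, ANCOVA power 80% to 87%, gain 1.3 to 8.0 points. In change-score terms this is a trial of about 52 to 62 patients (50/(ratio × 47/46)).
- Latent SD 4 or 6 at both times: gain 1.1 to 9.9 points.
- Latent SD 5 at baseline and 6 to 7 at follow-up: −0.9 to +4.6 points.
- If 0.80 is on the follow-up SD instead (latent SD 5 at both times): planned power 71% to 90%, gain 1.1 to 8.7 points.

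In the simulation with latent SD 5 at both times, rejection under the null was 0.048 to 0.051 for both tests.

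**6. If all visits enter.** With eight time levels, equal SDs, compound symmetry and ρ = 0.5 (all assumed), the 7-df interaction had 77% to 78% power. ANCOVA at 4 months has about 89% under the same equal-SD, ρ = 0.5 assumption.

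**The case against.** The strongest reply is that nothing is broken. The planned test is valid and unbiased, and the choice lies between two accepted analyses of the same arm difference. That stands, and this point claims no more than an improvement.

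Second, the size of the gain is uncertain. Uneven response to treatment could widen the follow-up SD and push the slope towards 1. Five of the twelve cells in the table show a loss. This also stands, and it is why the range starts below zero. The losses stay under 1 point, so the balance still favours adjustment.

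Third, the gap between 79% and 80% is at rounding level, and 79% assumes no drop-out. Agreed: the case rests on the cheap gain, not on crossing 80%.

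A reader might infer several stronger things that the documents do not support:
- That the primary test simply is a t test on change. Data Analysis does not list the time points, and a single ISI score may only mean one instrument.
- That power would rise to 84% to 92%. Those figures need equal baseline and follow-up SDs (ρ = 0.7 down to 0.3), which an entry threshold on baseline ISI makes unlikely.
- That every outcome should be adjusted in the same way. The protocol lists several baselines after randomization, including those for diary-based primary endpoints.

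**Conclusion.** The point holds as a free improvement. Baseline-adjusted analysis targets the same 4-month arm difference with a large-sample variance that is never higher, and it removes the doubt about what time means. At 25 per group and 0.80 on the change SD, power moves from 79% by between about −1 and +8 points under the main assumptions (latent SD near 5 at baseline, ρ 0.3 to 0.7, entry at ISI 15 or more). It reaches nearly +10 if the latent SD is 4 at both times. The direction is well supported unless the true slope is near 1. The size is not, because the documents give neither SDs nor a correlation. The figures assume that all 50 patients are analysed.

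**What to change.** Replace the primary analysis sentence with one that specifies:
- the arm difference in ISI at the week 14-16 visit;
- an ANCOVA with arm and baseline ISI, two-sided 0.05;
- baseline defined as the intake/eligibility ISI obtained before randomization.

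The group-by-time model, with its visits named, can stay as a supportive analysis. Apply the same approach to other outcomes only where the baseline precedes randomization, such as the ESS score used for exclusion and the diagnostic sleep study. For the diary, Global Morning Rating, III and FSS, the baseline would first have to be completed before allocation.

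Cost: one degree of freedom (47 instead of 48) and a change of wording, with no new patients, visits or data for ISI. If the true slope is near 1, power falls by under 1 point. The change does not settle how patients without a week 14-16 ISI enter the ITT analysis. The plan needs to state that under either method.

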#### **Risks/Benefits:**

##### **Risks:**

The study is considered to be of low risk to subjects in that PAP Therapy will be used as indicated according to the instructions for use, and study devices will be dispensed by trained clinic staff, who will also oversee the subjects throughout the course of their study participation. Safety events

reported by subjects and observed by the investigator and study staff will be carefully reviewed and treated as required by the Patient Safety Advocate.

#### **Adverse Events and Adverse Device Effects**

An Adverse Event (AE)/Adverse Device Effect (ADE) is any untoward occurrence in a subject or clinical investigation where the subject has been administered an investigational product and which does not necessarily have a causal relationship with this product. An AE/ADE can therefore be any unfavorable and unintended sign (including an abnormal laboratory finding), symptom, or disease temporally associated with the use of an investigational product or clinical investigation procedure, whether or not related. At each evaluation, the investigator will determine whether any adverse events (AEs) or adverse device effects (ADEs) have occurred. For the purpose of this protocol, an adverse event and adverse device effect is any undesirable clinical occurrence in a subject that can be attributed to the device or procedure required by this protocol.

Certain adverse effects are anticipated with the use of PAP therapy. Expected adverse effects are usually mild in intensity and resolve within 24 hours after discontinuing the use of the device. The following adverse effects may occur:

- Drying of the nose, mouth or throat
- Nosebleed
- Ear or sinus discomfort
- Eye irritation
- Skin rashes

Anticipated adverse effects that are mild in intensity and resolve within 24 hours do not need to be recorded in the case report forms (CRFs).

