**Quality of Life Enjoyment and Satisfaction Questionnaire (QLESQ)-Summary Sheet:** QLESQ is a 17 question survey measuring current life satisfaction. It is an abbreviated version of the full QLESQ and is an expedient and satisfactory substitute for the full version.

**Hopkins Symptom Checklist (HSCL):** This well-known and widely used 25-item inventory measures symptoms of anxiety and depression. Part I of the HSCL has 10 items for anxiety symptoms and Part II of the HSCL has 15 items for depression symptoms. All questions are measured on a four point scale ranging from “Not at all” to “Extremely”.

**Patient Global Assessment of Sleep (PGA):** The PGSA consists of 5 question subjectively assessing daytime and nighttime insomnia symptom improvement (or worsening) on a percent scale in comparison to the intake assessment.

**PAP Units of Distress Survey (PUDS):** The PUDS is a scale of 0-10 measuring current subjective distress as it relates to PAP therapy. This survey is based on the Subjective Units of Distress Scale (SUDS) typically used in a clinical desensitization-based therapy setting to evaluate treatment progress.

**Adverse Effects Checklist (AEC):** This checklist consists of common side effects or adverse experiences common to new PAP users. Symptoms are categorized into three groups: mask problems, pressure problems, or other problems. The checklist will facilitate discussion with the patient at follow-up.

**NOSE-8:** This 8 question survey queries patients on congestion, stuffiness, or runny nose symptoms as they relate to sleep and PAP use on a 5 point Likert scale. This questionnaire also measures subjective treatment efficacy of these symptoms.

**Intake Supplement:** This questionnaire is a baseline assessment of the patient's understanding of the treatment rationale and their views on PAP and sleep medication, so that we can compare any changes in views at the exit interview.

**Exit Interview Questionnaire (EIQ):** This questionnaire is an assessment of the patient's perception of the study including: general overview, treatment rationale, effectiveness of PAP therapy, PAP and sleep medication, long-term treatment of SDB, and PAP devices and masks.

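### The protocol defines an adverse event in two incompatible ways, and its protocol-specific sentence leaves events judged unrelated with no requirement to be recorded

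*Combined protocol and SAP*

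**What the plan says.** All the definitions stand in one paragraph of Adverse Events and Adverse Device Effects, under Risks/Benefits.

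- The opening definition covers AEs and ADEs together and describes an occurrence "which does not necessarily have a causal relationship with this product". It extends to any unfavourable sign, "symptom, or disease temporally associated with the use of an investigational product or clinical investigation procedure, whether or not related".
- Next comes the person who decides: at each evaluation "the investigator will determine whether any adverse events (AEs) or adverse device effects (ADEs) have occurred".
- The sentence after that redefines both terms, expressly for this trial: "an adverse event and adverse device effect is any undesirable clinical occurrence in a subject that can be attributed to the device or procedure", meaning a procedure that the protocol requires.

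The same section then lists anticipated effects of PAP and says that those that are "mild in intensity and resolve within 24 hours do not need to be recorded in the case report forms".

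Follow-up Visits (Phase 3) asks at each visit whether any AE or ADE has occurred and gives no definition of its own. The Adverse Effects Checklist (AEC) is among the questionnaires patients complete at those visits. Under Questionnaires it is described as covering effects common in new PAP users, and its purpose is given as "The checklist will facilitate discussion with the patient at follow-up".

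**The concern.** Relatedness is normally a judgement recorded about an event after the event has been captured. In the protocol-specific sentence it becomes a condition for being an adverse event at all. If staff follow that sentence, an event judged unrelated never enters the AE record, and the judgement cannot be revisited when the trial is analysed or when a pattern appears across patients.

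Two features add to this. First, AE and ADE are one category under either definition, so the record as defined does not separate related from unrelated events. Second, attribution is decided at the site, where the arm is very probably known. What is recorded could then differ between CPAP and ASV for reasons other than what happened to patients. It is the safety comparison that is at stake, not efficacy.

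**Working it through.** No arithmetic applies: the plan gives no adverse event rate, count or analysis to reproduce. The check sets the texts side by side.

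**1. The two definitions applied to the same event**

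| Investigator's view of the event | Opening definition | Protocol-specific sentence |
|---|---|---|
| Attributable to device or procedure | AE/ADE | AE/ADE |
| Not attributable | AE/ADE | Neither |

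The second row is the contradiction. The lead-in to the later sentence marks it as the one governing this protocol, so a careful reader would take the narrower wording as operative.

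**2. Does another section resolve it?** Follow-up Visits uses both terms without defining them. Risks says that safety events reported by subjects or seen by staff are reviewed and treated; it does not limit this to related events, but it does not say they are recorded. Neither section settles the matter.

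**3. Is an unrelated event required to be recorded by another route?**

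- The AEC is patient-completed, but it is confined to effects common in new PAP users.
- The daily distress score in the Sleep Diary (PUDS) concerns PAP only.
- Supplemental Follow-up Care sends pressure intolerance, mask, leak and other adaptation problems to the CRFs; these too are PAP problems.
- The Sleep Diary prompts patients to flag changes such as medication. That might bring an unrelated event to light, but it is not an adverse event entry.

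None of these requires an event judged unrelated to be recorded as such.

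**4. Who applies the attribution condition, and do they know the arm?** The investigator decides. Blinding is stated for the independent sleep-study scorer only (Titration #1 and Polysomnography). The physician reviews each titration and prescribes the settings (Titration #1). The research coordinator sets the device to the assigned mode (Set-up), and follow-up visits are held with a clinical research coordinator (Clinic Follow-up). Knowledge of the arm is an inference from these roles, though a well-supported one.

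**5. Is any safety tabulation planned?** Summary of Endpoint Objectives places the AEC among the other tracking variables and lists no adverse event endpoint. Data Analysis names no adverse event or AEC analysis.

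**The case against.** The strongest reply is that the trial collects a good deal of tolerability data that never passes through the AE definition. The AEC appears with the outcome questionnaires in Follow-up Visits and again under Outcomes and Scales. Patients complete it themselves, and Data Collection and Storage has them entering data straight into the database, so investigator attribution does not filter it. PUDS is rated daily, and adaptation problems go to the CRFs. Staff might also apply the broader definition, or read the words about attribution generously, as covering anything that could conceivably be related.

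Most of this stands, and it rules out several stronger readings.

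- A reader might infer that the CPAP–ASV tolerability contrast rests on the adverse event record. It does not: pressure intolerance, which drives the trial's rationale, is captured by the routes just named.
- A reader might infer that all mild, short-lived effects are lost. The 24-hour rule says only that such entries are not needed, it is confined to anticipated effects, and the AEC still asks about common ones. The text does not say how an effect that recurs nightly is handled. The rule is a stated recording choice and not part of the contradiction.
- A reader might take the site's expectation of less intolerance with ASV (Titration #1) as an expectation about adverse events generally. It concerns pressure intolerance only.

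What the reply does not reach is the event judged unrelated. Even a generous reading of attribution excludes an event the investigator considers clearly unrelated, and none of the other instruments is designed to record it. Leaving staff to choose between two definitions also means that recording may vary between assessors or over time.

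**Conclusion.** The concern holds for events judged unrelated. The section contradicts itself, no other part of the document reconciles it, and the sentence presented as specific to this protocol leaves such events outside the AE record. The record is liable to be incomplete; whether it would be depends on which definition staff apply.

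The size cannot be given. The documents contain no expected adverse event counts, and converting a few hypothetical events in arms of about 25 into percentages would not measure the loss. The possibility of differential recording by arm rests on the inference that those attributing events know the assignment; the documents do not say so outright. The ISI comparison and the other efficacy outcomes are not affected. This is an internal inconsistency that should be corrected, because events not captured during conduct cannot reliably be recovered afterwards.

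**What to change.** Reconcile the section to one definition:

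- An AE is any untoward occurrence, recorded whether or not it is thought related.
- Relatedness to device or procedure is a separate CRF field, ideally assessed without knowledge of the PAP mode.
- An ADE is the subset of AEs judged related to the device or a protocol procedure.

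Refer to that definition in Follow-up Visits. Add to Data Analysis a descriptive tabulation, by randomised arm, of AEs, ADEs and the AEC items already collected.

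The cost is a wording change, one CRF field, and a small amount of extra recording and tabulation. No treatment or clinical management rule changes.

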### **Follow-up Visits**

Participants will return every 2 weeks following their titration study for a follow-up clinic appointment conducted by sleep technologist with availability of [name] for relevant Q&A with patient. The following will be completed at each follow-up appointment:

1. Outcomes: Subject completes the following questionnaires:
  - a. Validated research instrument for tracking insomnia: ISI
  - b. Sleep related impairment: ESS, VAS-F, VAS-S, III, FSS, SDB-6
  - c. Quality of Life/Impairment: FOSQ-10, QLESQ, HSCL
  - d. PAP Therapy Tracking Tools: AEC, NOSE-8
  - e. Change Tracking Tool: PGA (Insomnia, Sleep Quality, Fatigue, Sleepiness, Energy level)
2. Data, download from the VPAP Adapt.
  - a. Usage
  - b. AHI, flattening %
3. Review device usage. Address concerns or questions including:
  - a. Progress and experiences with PAP
  - b. Benefits or lack thereof
4. Review sleep diary.
5. Determine if the subject has had any adverse events or adverse device effects.
  - a. Troubleshoot as needed

**Summary:** Following initial titration, the following steps will reoccur for the remainder of the protocol (refer to initial flow chart to see repetition of steps):

- Patients return on weeks 2 and 4 for Follow-up visits
- On week 6 they repeat titration process and complete Follow-up visit surveys and downloads
- Return on weeks 8 and 10 for follow-up appointments
- Return on week 12 for a final titration

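### The adverse-event section gives two incompatible definitions, and the one that reads as operative leaves events judged unrelated with no stated route into the adverse-event record

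*Combined protocol and SAP*

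**What the plan says.** All of the defining text is in the protocol section Adverse Events and Adverse Device Effects, under Risks/Benefits.

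- **Broad definition.** An AE/ADE is an untoward occurrence "which does not necessarily have a causal relationship with this product". The next sentence extends this to any unfavourable sign, symptom or disease "temporally associated with the use of an investigational product or clinical investigation procedure, whether or not related".
- **Narrow definition.** Two sentences later, in the same paragraph and expressly for this protocol, the text says: "an adverse event and adverse device effect is any undesirable clinical occurrence in a subject that can be attributed to the device or procedure".
- **Who decides.** "At each evaluation, the investigator will determine whether any adverse events (AEs) or adverse device effects (ADEs) have occurred". The Follow-up Visits section gives staff the matching task: "Determine if the subject has had any adverse events or adverse device effects".

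Three other places bear on the point. The Adverse Effects Checklist (AEC) is described under Questionnaires: "This checklist consists of common side effects or adverse experiences common to new PAP users". It is completed at each follow-up visit, as are NOSE-8 and the HSCL. Supplemental Follow-up Care has PAP concerns, and how they were handled, written into study documents and case report forms. The Risks section says that safety events will be reviewed and treated, but gives no rule for recording them.

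**The concern.** Both definitions are current text, and they classify the same event differently. Two coordinators following this section in good faith could keep different safety records. Because the narrow definition is introduced as the one for this protocol, a careful reader would take it as binding.

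Good practice is to log the event and then judge whether it is related. Under the narrow definition the judgement comes first and decides whether there is an adverse event at all. An unexpected harm is the kind least likely to be linked to the device when it first appears, so it is the kind most exposed to this rule. An event that was never logged cannot be reclassified later.

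The narrow definition also leaves no category for an unattributed event. Staff are asked about adverse events or adverse device effects as if these were two things, yet both carry the same attribution condition.

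**Working it through.** The plan states no figure on this point, so there is none to reproduce. The check is a reading of the rules against example records.

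**Step 1: apply both definitions.**

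| Example record | Broad definition | Narrow definition | Other stated capture |
|---|---|---|---|
| Nosebleed attributed to the mask | AE/ADE | AE/ADE | On the list of anticipated effects; the separate exemption for mild effects resolving within 24 hours may apply |
| New palpitations, judged unrelated | AE/ADE | Not an AE/ADE | None stated, assuming palpitations are not a checklist item (the item list is not in the documents) |
| Worsening mood, cause uncertain | AE/ADE | Depends on whether it can be attributed | Symptom score on the HSCL at each follow-up, not labelled an AE |

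The definitions agree on the first record, disagree on the second and may disagree on the third. The gap is therefore events judged unrelated that no other instrument picks up.

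**Step 2: look for a rule that closes the gap.** The AEC covers effects common in new PAP users (mask, pressure and other problems), and its stated use is to support discussion. NOSE-8 covers nasal symptoms. The HSCL covers anxiety and depression. Supplemental Follow-up Care covers PAP concerns. The daily diary asks whether something, such as medication, has changed. None of these requires an off-list event judged unrelated to be logged as an adverse event.

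**Step 3: who judges, and with what knowledge.** The investigator determines whether an event has occurred. The only masking stated is that of the technologist who scores the sleep studies (Titration #1; Polysomnography). The physician reviews the titration done in the assigned mode and prescribes settings, and the coordinator sets the mode on the device (Set-up). That the judgement is unmasked is a sound inference, but it is not stated.

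**Step 4: is a comparison planned?** Adverse events are not among the primary or secondary endpoints. The AEC is listed under Other Tracking Variables. Data Analysis names no comparison of adverse events between arms.

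**Step 5: illustration only.** Apart from the planned 25 patients per arm, every input is assumed. Expected patients with a recorded event = 25 × true risk × probability of attribution. With a true risk of 40% in both arms, 25 × 0.40 = 10 patients per arm have an event. The last column is the chance of a two-sided Fisher exact p ≤ 0.05, summed over all pairs of binomial counts.

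| Attribution, arm 1 / arm 2 | Expected recorded | Chance of p ≤ 0.05 |
|---|---|---|
| All events recorded | 10 v 10 | 0.03 |
| 50% / 50% | 5 v 5 | 0.02 |
| 30% / 70% | 3 v 7 | 0.19 |
| 20% / 80% | 2 v 8 | 0.45 |

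Equal attribution loses events but creates no false difference. Only attribution that differs by arm can create one, and the documents do not show that it would differ.

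**The case against.** The strongest reply is that this is a drafting slip with limited reach. Four stronger readings are tempting, and the documents do not support them.

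- **That every unattributed event is lost.** The AEC, NOSE-8 and HSCL are completed at each follow-up with no attribution step, and PAP concerns that prompt extra care go into the case report forms. Worsening mood, for example, would show in the HSCL, which is a secondary endpoint. The wording is also that an event *can be* attributed, which is looser than *is* attributed, so an event of uncertain cause may still qualify. All of this stands, and it confines the gap to events that are judged unrelated and fall outside these instruments.
- **That a planned comparison of adverse events between arms is biased.** None is planned. The point touches only a tabulation that someone might make later.
- **That staff will attribute more events to CPAP because the protocol expects it to be less well tolerated.** The Background and Titration #1 predict expiratory pressure intolerance on CPAP. That is plainly related to the device in either arm. It says nothing about how unrelated-looking events would be judged.
- **That a false difference of a particular size should be expected.** The documents give no event rate and no attribution rate, so any such figure only restates its assumptions.

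None of this removes the contradiction. The other instruments record symptoms, not adverse events, and none supplies the missing rule for an off-list event judged unrelated.

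**Conclusion.** The concern holds as an internal contradiction with a practical consequence. The protocol defines an adverse event in two incompatible ways. The narrower definition reads as operative, and following it leaves an off-list event judged unrelated with no stated route into the adverse-event record. Neither definition separates an adverse event from an adverse device effect, and the narrow one leaves no place for events outside the attributed set.

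The number of events affected cannot be estimated from the documents. Distortion between arms is a possibility for a later tabulation, not a demonstrated bias. It would need attribution to differ by arm, and it rests on the inference that the investigator knows the mode. The conclusion also assumes that the checklist items do not already cover the event in question. The section should be corrected, but no planned analysis is invalidated.

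**What to change.** In the section Adverse Events and Adverse Device Effects:

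1. Delete the sentence that narrows the definition for this protocol.
2. Keep the any-causality definition for adverse events.
3. Define an adverse device effect as the subset attributed to the device or to a protocol procedure.
4. Add a relatedness field to the case report form, completed after the event has been logged.
5. If adverse events are tabulated by arm, show all of them before the device-effect subset. This does not require a new planned analysis.

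The exemption for mild anticipated effects is a separate rule, and this change leaves it alone.

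The cost is a wording change, one form field and slightly more event entries. Staff already ask about adverse events at every follow-up, so no extra visits are needed.
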